9.5.2 Auxiliaries supplied by site

• Glucagon for injection (reimbursed by Novo Nordisk affiliate, supplied by the central lab in Russia)

9.5.3 Continuous glucose monitoring equipment supplies

Novo Nordisk will provide the following:

Protocol Trial ID: NN1218-3854 UTN: U1111-1118-2480 EnderCT pp.: 2010-024054-11	CONFIDENTIAL	Date: Version: Status:	4.0 Final	Novo Nordisk
EudraCT no.: 2010-024054-11		Page:	84 of 149	

- CGM device (receiver and transmitter)
- CGM user guide and quick user guide (for site use)
- Instructions for Subjects

CGM equipment should be returned to Novo Nordisk at end of treatment (Visit 22).

The CGM manufacturer will provide the following:

- CGM installation link to CGM software
- CGM sensors (customs clearance must be expected)
- CGM training (webinar or on-site)

A PC with internet connection must available at site (same PC as used for the eCRF system can be utilised). For further instruction and requirements, please see CGM manufacturer's user guide.

 Trial ID: NN1218-3854
 CONFIDENTIAL
 Version: 4.0

 UTN: U1111-1118-2480
 Status: Final

 EudraCT no.: 2010-024054-11
 Page: 85 of 149

10 Interactive voice/web response system

A trial-specific IV/WRS will be set up which can be accessed at any time via the internet or telephone. Access to the IV/WRS must be restricted to and controlled by authorised persons.

IV/WRS is used for:

- Screening
- Screening / Run-in failure
- Randomisation
- Medication arrival
- Dispensing
- Discontinuation from trial product
- Completion
- Code break
- Drug accountability
- Data change

IV/WRS user manuals will be provided to each trial site.

 Trial ID: NN1218-3854
 CONFIDENTIAL
 Version: Status: Final Page:
 4.0

 UTN: U1111-1118-2480
 Status: Final Page:
 86 of 149

11 Randomisation procedure and breaking of blinded codes

At randomisation (Visit 6) the Subject will be randomised to either faster-acting insulin aspart or NovoRapid[®] in a 1:1 manner to the two different treatment arms described below using the IV/WRS:

- Faster-acting insulin aspart
- NovoRapid[®]

The randomisation will be stratified based on the following factor:

• Use of own CGM (Yes/No)

11.1 Breaking of blinded codes

The code for a particular Subject may be broken in a medical emergency if knowing the actual treatment would influence the treatment of the Subject. Whenever a code is broken the person breaking the code must print the Code Break Confirmation Notification generated by the IV/WRS, record the reason, and sign and date the document.

The IV/WRS will notify Novo Nordisk (monitor and the Global Safety department) immediately after the code is broken.

When the code is broken, the treatment allocation will be accessible to the Investigator and the Novo Nordisk Global Safety department. If IV/WRS is not accessible at the time of code break the IV/WRS helpdesk should be contacted. Contact details are listed in Attachment I.

If the code has been broken the Subject must be discontinued from trial product and a discontinuation session must be completed in IV/WRS.

 Trial ID: NN1218-3854
 CONFIDENTIAL
 Version: 4.0

 UTN: U1111-1118-2480
 Status: Final

 EudraCT no.: 2010-024054-11
 Page: 87 of 149

12 Adverse events, technical complaints and pregnancies

12.1 Definitions

12.1.1 Adverse events

An AE is any untoward medical occurrence in a Subject administered a product, and which does not necessarily have a causal relationship with this treatment.

An AE can therefore be any unfavourable and unintended sign (including an abnormal laboratory finding), symptom or disease temporally associated with the use of a product, whether or not considered related to the product.

An AE includes:

- A clinically significant worsening of a concomitant illness
- A clinical laboratory AE (CLAE): a clinical laboratory abnormality which is clinically significant, i.e. an abnormality that suggests a disease and/or organ toxicity and is of a severity that requires active management. Active management includes active treatment or further investigations, for example change of medicine dose or more frequent follow-up due to the abnormality

The following should **not** be reported as AEs:

- Pre-existing conditions, including those found as a result of screening procedures (pre-existing conditions should be reported as medical history or concomitant illness)
- Pre-planned procedures unless the condition for which the procedure was planned has worsened from signing the SI/IC
- Non-serious hypoglycaemia is an AE but is reported on a Hypoglycaemic Episode Form instead of on an AE Form; please see section 8.3.3.1
- Non-serious unexplained hyperglycaemias are AEs, but are reported on a Unexplained Hyperglycaemic Form instead of on an AE Form; please see section 8.3.3.2

The following three definitions are used when assessing an AE:

• Severity

- Mild no or transient symptoms, no interference with the Subject's daily activities
- **Moderate** marked symptoms, moderate interference with the Subject's daily activities
- Severe considerable interference with the Subject's daily activities; unacceptable

Causality

The following terms are used when assessing the relationship between an AE and the relevant trial product(s):

Trial ID: NN1218-3854 UTN: U1111-1118-2480 EudraCT no.: 2010-024054-11 Version: 4.0 Status: Final Page: 88 of 149

• **Probable** - good reason and sufficient documentation to assume a causal relationship

- Possible a causal relationship is conceivable and cannot be dismissed
- Unlikely the event is most likely related to aetiology other than the trial product

• Final outcome:

- **Recovered/resolved** the Subject has fully recovered, or by medical or surgical treatment the condition has returned to the level observed at the first trial-related activity after the Subject signed the informed consent
- Recovering/resolving the condition is improving and the Subject is expected to recover from the event. This term is only applicable if the Subject has completed the trial or has died from another AE
- Recovered/resolved with sequelae the Subject has recovered from the condition, but with lasting effect due to a disease, injury, treatment or procedure. If a sequela meets an SAE criterion, the AE must be reported as an SAE
- **Not recovered/not resolved** the condition of the Subject has not improved and the symptoms are unchanged, or the outcome is not known
- Fatal this term is only applicable if the Subject died from a condition related to the reported AE. Outcomes of other reported AEs in a Subject before he/she died should be assessed as "recovered/resolved", "recovering/resolving", "recovered/resolved with sequelae" or "not recovered/not resolved". An AE with fatal outcome must be reported as an SAE
- Unknown this term is only applicable if the Subject is lost to follow-up

12.1.2 Serious adverse events

A SAE is an experience that at any dose results in any of the following:

- Death
- A life-threatening^a experience
- In-patient hospitalisation or prolongation of existing hospitalisation
- A persistent or significant disability or incapacity^c
- A congenital anomaly or birth defect
- Important medical events that may not result in death, be life threatening^a or require hospitalisation^b may be considered an SAE when based on appropriate medical judgement they may jeopardise the Subject and may require medical or surgical intervention to prevent one of the outcomes listed in the definition of SAE^d

Protocol Date: 04 February 2016 Novo Nordisk
Trial ID: NN1218-3854 Version: 4.0

Final

89 of 149

UTN: U1111-1118-2480 CONFIDENTIAL Version: Status: Page:

The following adverse events must always be reported as a Serious Adverse Event using the important medical event criteria if no other seriousness criteria are applicable:

- Suspicion of transmission of infectious agents via the trial product
- Risk of liver injury defined as ALT or AST >3 x UNL and total bilirubin > 2 x UNL, where no alternative aetiology exists (Hy's law)
- a. The term "life threatening" in the definition of SAE refers to an event in which the Subject was at risk of death at the time of the event. It does not refer to an event which hypothetically might have caused death if it was more severe
- b. The term "hospitalisation" is used when a Subject:
 - Is admitted to a hospital or in-patient, irrespective of the active of physical stay, or
 - Stays at the hospital for treatment or observation for more than 24 hours

Medical judgement must always be exercised, and when in doubt, the hospital contact should be regarded as a hospitalisation. Hospitalisations for administrative, trial-related and social purposes do not constitute AEs and should therefore not be reported as AEs or SAEs. Hospital admissions for surgical procedures, planned before trial inclusion, are not considered AEs or SAEs

- c. A substantial disruption of a Subject's ability to conduct normal life functions (e.g. following the event or clinical investigation the Subject has significant, persistent or permanent change, impairment, damage or disruption in his/her body function or structure, physical activity and/or quality of life)
- d. For example intensive treatment in an emergency room or at home of allergic bronchospasm, blood dyscrasiasis or convulsions that do not result in hospitalisation, or development of drug dependency or drug abuse

12.1.3 Non-serious adverse events

A non-serious AE is any AE which does not fulfil the definition of an SAE.

12.1.4 Medical events of special interest

A MESI is an event which, in the evaluation of safety, has a special focus. A MESI is an AE (SAE or non-serious AE) which fulfils the below defined MESI criteria.

- Medication errors concerning trial products:
 - Administration of wrong drug (Note: Use of wrong DUN is not considered a medication error.)
 - Wrong route of administration, such as intramuscular instead of s.c.
 - Administration of an overdose with the intention to cause harm (e.g. suicide attempt)

Protocol		Date:	04 February 2016	Novo Nordisk
Trial ID: NN1218-3854	CONFIDENTIAL	Version:	4.0	
UTN: U1111-1118-2480	CONFIDENTIAL	Status:	Final	

• Accidental administration of a lower or higher dose than intended. The administered dose must deviate from the intended dose to an extend where clinical consequences for the trial Subject were likely to happen as judged by the Investigator, although not necessarily did happen

Page:

90 of 149

12.1.5 Technical complaint

A technical complaint is any written, electronic, or oral communication that alleges product (medicine or device) defects. The technical complaint may be associated with an AE, but does not concern the AE itself

Examples of technical complaints:

EudraCT no.: 2010-024054-11

- The physical or chemical appearance of trial products in the vials (e.g. discoloration, particles or contamination)
- The 10 mL vial packaging material (e.g. leakage, cracks, rubber membrane issues or errors in labelling text)

However, colour change, particle or crystal formation in the infusion set and reservoir are not considered as a technical complaint and thereby not to be reported to Customer Complaint Centre, Novo Nordisk

12.2 Reporting of adverse events

All events meeting the definition of an AE must be collected and reported. This includes events from the first trial-related activity after the Subject has signed the SI/IC until the last phone contact/site visit. The events must be recorded in the applicable eCRF form in a timely manner; see timelines below and in Figure 12–1.

During each contact with the trial site staff, the Subject must be asked about AEs and technical complaints, for example by asking: "Have you experienced any problems since the last contact?"

All AEs, observed by the Investigator or Subject, must be reported by the Investigator and evaluated. Novo Nordisk assessment of expectedness is performed according to the following reference documents:

- Faster-acting insulin aspart: IB, current version and updates thereof
- Insulin aspart (NovoRapid®): Company Core Data Sheet (CCDS) Current version

All AEs must be recorded by the Investigator on an AE Form. The Investigator should report the diagnosis, if available. If no diagnosis is available, the Investigator should record each sign and symptom as individual AEs using separate AE Forms.

For SAEs, a SIF must be completed in addition to the AE Form. If several symptoms or diagnoses occur as part of the same clinical picture, one SIF can be used to describe all the SAEs.

Protocol		Date:	04 February 2016	Novo Nordisk
Trial ID: NN1218-3854	CONFIDENTIAL	Version:	4.0	
UTN: U1111-1118-2480	CONFIDENTIAL	Status:	Final	
EudraCT no.: 2010-024054-11		Page:	91 of 149	

MESIs, regardless of seriousness, must be reported using the AE Form, the SIF and a MESI Form. The MESI Form is a form tailored to collect specific information related to the individual MESI.

The AE Form for a non-serious AE not fulfilling the MESI criteria should be signed when the event is resolved or at the end of the trial.

12.2.1 Timelines for initial reporting of adverse events

The Investigator must complete the following forms in the eCRF within the specified timelines:

• **SAEs** - The AE Form **within 24 hours** and the SIF **within five calendar** days of the Investigator's first knowledge of the SAE

Both forms must be signed within seven calendar days from the date the information was entered in the eCRF:

- SAEs fulfilling the MESI criteria In addition to above, the MESI Form within 14 calendar days of the Investigator's first knowledge of the AE
- Non-serious AE fulfilling the MESI criteria The AE Form, SIF and MESI Form within 14 calendar days of the Investigator's first knowledge of the event

If the eCRF is unavailable, the concerned AE information must be reported on paper forms and sent to Novo Nordisk by fax, e-mail or courier within the same timelines as stated above. When the eCRF becomes available, the Investigator must transcribe the information on the appropriate forms in the eCRF.

Contact details (fax, telephone, e-mail and address) are provided in the Investigators trial file.

[figure not shown]

Figure 12–1 Initial reporting of AEs

 Trial ID: NN1218-3854
 Version:
 4.0

 UTN: U1111-1118-2480
 Status:
 Final

 EudraCT no.: 2010-024054-11
 Page:
 92 of 149

12.2.2 Reporting of trial product-related SUSARs by Novo Nordisk

Novo Nordisk will notify the Investigator of trial product-related suspected unexpected serious adverse reactions (SUSARs) in accordance with local requirements and GCP¹. In addition, the Investigator will be informed of any trial-related SAEs that may warrant a change in any trial procedure.

In accordance with regulatory requirements, Novo Nordisk will inform the regulatory authorities, including EMA, of trial product-related SUSARs. In addition, Novo Nordisk will inform the Institutional Review Boards/Independent Ethics Committees (IRBs/IECs) of trial product-related SUSARs in accordance with local requirement and $GCP^{\underline{1}}$, unless locally this is an obligation of the Investigator.

12.2.3 Novo Nordisk products used as concomitant medication

If a SAE and/or MESI is considered to have a causal relationship with a Novo Nordisk marketed product used as concomitant medication in the trial, it is important that the suspected relationship is reported to Novo Nordisk, e.g. in the alternative aetiology section on the safety information form. Novo Nordisk may need to report this AE to relevant regulatory authorities.

12.3 Follow-up of adverse events

The Investigator must record follow-up information by updating the forms in the eCRF.

Follow-up information must be reported to Novo Nordisk according to the following:

- SAEs All SAEs must be followed until the outcome of the event is "recovered/resolved", "recovered/resolved with sequelae" or "fatal", and until all queries have been resolved. Cases of chronic conditions, cancer or AEs ongoing at time of death (where death is due to another AE) may be closed with the outcome "recovering/resolving" or "not recovered/not resolved". Cases can be closed with the outcome of "recovering/resolving" when the Subject has completed the follow-up period and is expected by the Investigator to recover. The SAE follow-up information should only include new (e.g. corrections or additional) information and must be reported within 24 hours of the Investigator's first knowledge of the information. This is also the case for previously non-serious AEs which subsequently become SAEs
- Non-serious AEs Non-serious AEs must be followed until the outcome of the event is "recovering/resolving", "recovered/resolved" or "recovered/resolved with sequelae" or until the end of the follow-up period stated in the protocol, whichever comes first, and until all queries related to these AEs have been resolved. Cases of chronic conditions, cancer or AEs ongoing at time of death (where death is due to another AE) may be closed with the outcome "recovering/resolving" or "not recovered/not resolved". Cases can be closed with the outcome of "recovering/resolving" when the Subject has completed the follow-up period and is expected by the Investigator to recover

Protocol	CONFIDENTIAL	Date:	04 February 2016	Novo Nordisk
Trial ID: NN1218-3854		Version:	4.0	
UTN: U1111-1118-2480		Status:	Final	
EudraCT no.: 2010-024054-11		Page:	93 of 149	

Non-serious AE fulfilling the MESI criteria - Non-serious AE fulfilling the MESI criteria must be followed as specified for non-serious AEs. Follow-up information on MESIs should only include new (e.g. corrections or additional) information and must be reported within 14 calendar days of the Investigator's first knowledge of the information. This is also the case for previously reported non-serious AEs which subsequently fulfil the MESI criteria.

The Investigator must ensure that the worst case severity and seriousness of an event is kept throughout the trial. A worsening of an unresolved AE must be reported as follow-up with re-assessment of severity and/or seriousness of the event.

Queries or follow-up requests from Novo Nordisk must be responded to within 14 calendar days from the date of receipt of the request, unless otherwise specified in the follow-up request.

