8.2.3 Concomitant illness and medical history

A **concomitant illness** is any illness, except T1DM, that is present at the start of the trial (i.e. at screening (Visit 1)) or found as a result of the screening procedures.

Any change to a concomitant illness should be recorded on the Concomitant Illness form in the eCRF during the trial. A clinically significant worsening of a concomitant illness must be reported as an AE as described in section 12.

Medical history is a medical event that the Subject has experienced in the past. Only relevant medical history, as judged by the Investigator, should be reported.

The information collected for concomitant illness and medical history should include diagnosis, date of onset, date of resolution, or continuation, as applicable.

Protocol Date: 04 February 2016 Novo Nordisk
Trial ID: NN1218-3854 Version: 4.0

Trial ID: NN1218-3854
UTN: U1111-1118-2480
EudraCT no.: 2010-024054-11

CONFIDENTIAL

Version:
Status:
Final
Page:
49 of 149

Concomitant illness and medical history must be recorded on the corresponding pages of the eCRF.

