2.4.2.2 Safety endpoints

All safety endpoints will be compared using the on-treatment observation period. In terms of adverse events, as a minimum, serious adverse events will be tabulated separately also using the in-trial observation period.

All events in the in-trial observation period will be listed with information about whether it appeared in the on-treatment observation period or not.

Number of treatment emergent Adverse Events (AEs)

AEs will be coded using the Medical Dictionary for Regulatory Activities (MedDRA). AEs will be presented based on system organ class and preferred terms.

A Treatment Emergent Adverse Event (TEAE) is defined as an event that has an onset date on or after the first day of exposure to randomised treatment, and no later than seven days after the last day of randomised treatment.

TEAEs are summarised descriptively, whereas AEs not defined as treatment emergent are presented in listings, including AEs reported in the 30-day follow-up period. The summaries of TEAEs are made displaying the number of Subjects with at least one event, the percentage of Subjects with at least one event, the number of events and the event rate per 100 patient years of exposure. These summaries are done by seriousness, severity, relation to insulin treatment, relation to technical complaint, premature treatment discontinuation due to AEs, AEs leading to withdrawal from trial and outcome.

Furthermore, summary tables based on system organ class and preferred terms are made for:

- All TEAEs
- Serious TEAEs
- Possibly or probably related TEAEs
- Severe TEAEs
- TEAEs with preferred term that are experienced by at least 5% of the Subjects in any treatment arm or by at least 5% of all Subjects

For AEs where additional information is recorded, this will be listed.

AEs occurring during the run-in period are considered non-treatment emergent and will be summarised separately.

Number of treatment emergent infusion site reactions

Infusion site reactions occurring during the trial will be summarised using the on-treatment observation periods, and listed.

Classification of Hypoglycaemia

Treatment emergent: hypoglycaemic episodes will be defined as treatment emergent if the onset of the episode occurs on or after the first day of IMP administration after randomisation and no later than one day after the last day on IMP.

Nocturnal hypoglycaemic episodes: are episodes occurring between 00:01 and 05.59 both inclusive.

[figure not shown]

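### Treatment emergence is judged by onset date alone, so on the natural reading an adverse event that begins before first trial product and worsens or turns serious on it stays out of the by-arm TEAE tables

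*Protocol*

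**What the plan says.** **Collection.** Protocol 12.2 on the AEs to be reported: "This includes events from the first trial-related activity after the Subject has signed the SI/IC until the last phone contact/site visit". AE records can therefore exist before any trial product is given at Visit 6.

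**Worsening.** Protocol 12.3 has follow-up recorded by updating the existing forms, and adds: "A worsening of an unresolved AE must be reported as follow-up with re-assessment of severity and/or seriousness of the event". It also says: "The Investigator must ensure that the worst case severity and seriousness of an event is kept throughout the trial". On the follow-up route for serious events it says: "This is also the case for previously non-serious AEs which subsequently become SAEs".

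**Treatment emergence.** SAP 2.4.2.2 and protocol 17.4.2.2 share one rule for what counts as a TEAE: "an event that has an onset date on or after the first day of exposure to randomised treatment". The window closes one week after randomised insulin stops. On earlier events the SAP says: "AEs occurring during the run-in period are considered non-treatment emergent and will be summarised separately". Other events that are not treatment emergent go to listings.

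**Tables.** The summaries by seriousness, severity, relation to insulin and premature discontinuation are all summaries of TEAEs, as are the tables by system organ class and preferred term. Serious events are also tabulated for the in-trial period, which starts at randomisation (protocol 17 and SAP 2, general considerations). SAP section 3, which lists the changes from the protocol, leaves the TEAE definition alone.

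**The concern.** Worsening on randomised insulin is a post-randomisation outcome. Comparing the safety of the two insulins is a stated secondary objective, and the TEAE tables are where general AEs are set side by side by arm. If a worsening is filed under an event that began before first dose, the classification follows the filing rule and not the time at which the harm occurred. The run-in summary would then carry a severity reached only on trial product, while the by-arm tables would omit it. Severe and serious events are likely to be few, so a handful of misplaced events matters most in those rows.

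**Working it through.** The documents give no figure for this point, so the check is mainly a reading of the rules, followed by an illustration of size on assumed rates.

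**1. The rule applied to cases.** Take first exposure as day 0 and last dose as day 112 (16 × 7). The written rule is: TEAE if 0 ≤ onset day ≤ 112 + 7 = 119.

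| Case | Onset day used | TEAE? | In-trial by onset? |
|---|---|---|---|
| Run-in onset day −14, serious on day 30, filed as follow-up | −14 | No | No |
| Same worsening filed as a new AE on day 30 | 30 | Yes | Yes |
| Screening onset day −35, serious on day 60, filed as follow-up | −35 | No | No |
| Onset on day 0 | 0 | Yes | Yes |

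The first two rows describe the same harm on the same day. Only the filing differs, and protocol 12.3 prescribes the filing in the first row.

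**2. Does another rule catch these events?** Protocol 8.2.3 says: "A clinically significant worsening of a concomitant illness must be reported as an AE". A concomitant illness is one present at the start of the trial or found through the screening procedures. An AE that begins later, in screening or run-in, is not covered. The extra table of serious events uses a period that starts at randomisation, and neither document says whether an event enters it by onset date or by the date it became serious.

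**3. Size per 100 TEAEs.**

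Inputs from the documents:
- Run-in: 4 weeks.
- Visit 2: nominally 2 weeks after screening, at most 17 days after it.
- TEAE window: 16 weeks + 7 days = 17 weeks.

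Assumptions, none of them in the documents:
- AE incidence is constant over time.
- 10–30% of pre-dose AEs are unresolved at Visit 6.
- 5–20% of those worsen later, by any grade.

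Formula: 100 × (pre-dose weeks / 17) × unresolved fraction × worsening fraction.

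- Low: 100 × 4/17 × 0.10 × 0.05 = 100 × 0.235 × 0.005 = 0.12.
- High, 6 weeks: 100 × 6/17 × 0.30 × 0.20 = 100 × 0.353 × 0.06 = 2.1.
- High, longest window: (17 + 28)/7 = 6.43 weeks, and 100 × 6.43/17 × 0.06 = 100 × 0.378 × 0.06 = 2.3.

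**4. Size in subjects.** With other assumed rates (5–20% of the 450 subjects with an AE ongoing at randomisation, 2–10% of those worsening), the count over both arms runs from 450 × 0.05 × 0.02 = 0.45 to 450 × 0.20 × 0.10 = 9.

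**The case against.** The strongest objection is that the key step is inferred. No text says that the onset date stays fixed when follow-up is entered, and the form instructions are not in the documents. That stands as a qualification. Still, an update to an existing event naturally keeps that event's onset, and nothing resets the date or captures a date of worsening. The same holds for the in-trial table of serious events: exclusion follows if events are allocated by onset, which the plan leaves open.

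A second objection is that little turns on it. The rule is the same in both blinded arms and the TEAE tables carry no test. A hypoglycaemic episode form covers at most 60 minutes and an unexplained hyperglycaemic episode at most 24 hours, so almost none can straddle first dose. An AE that becomes serious must still be reported within 24 hours, and the safety committee and data monitoring committee review safety data throughout. All of this is right, and it keeps the point small.

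Third, the concomitant-illness rule need not be inconsistent with 12.3, because a pre-existing illness has no AE record to update. That is a fair reason for the different filing. It does not justify the different treatment of worsening in the analysis.

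A reader might go further and infer three things that the documents do not support:

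- **That differences in infusion site reactions are hidden.** The infusion set and reservoir are changed when trial product starts at Visit 6, and sites are rotated afterwards with routine changes at intervals of no more than 3 days (protocol 8.1.4 and 8.3.2.3). A reaction at a new site would ordinarily be a new event with its own onset.
- **That the missed events all fall in the severe and serious rows.** Mild-to-moderate worsening is missed too and touches neither row.
- **That the events vanish.** They remain in the run-in summary or in listings.

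**Conclusion.** The gap is real and follows from the written definitions, given the natural reading that a follow-up entry keeps the event's onset date. An AE that begins between consent and first trial product and worsens or becomes serious on randomised insulin does not enter the by-arm TEAE, severe TEAE or serious TEAE tables. On allocation by onset date it also misses the in-trial table of serious events. The likely size is low, about 0.1 to 2 per 100 TEAEs, or roughly 0.5 to 9 subjects among 450. Both ranges rest wholly on the assumed rates shown above. No efficacy analysis and no formal safety model is affected. It is worth correcting because it is cheap and because the counts it touches include serious events.

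**What to change.** **TEAE definition (protocol 17.4.2.2 and SAP 2.4.2.2).** Add: *or an event with onset before first exposure that increases in severity or becomes serious between the first day of exposure and seven days after the last day of randomised treatment.*

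**In-trial table of serious events.** State that an earlier-onset event enters by the date on which it worsened or became serious.

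**Data capture (protocol 12.3).** Choose one of two routes, not both:

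- Keep the single record and the worst-case rule, and add to the AE form the date of worsening or of becoming serious and the severity at first trial product. This is the simpler route.
- Require a new AE record for a worsening after first dose, and amend the worst-case sentence so that the earlier record may keep its pre-treatment severity. Without that amendment the two instructions in 12.3 would conflict.

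**Cost.** One clause in each definition, one sentence on the in-trial table and, on the first route, two extra items on the AE form. A few events will appear in both the run-in summary and the TEAE tables, which a footnote can explain.
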